6.2.4. Sample Size Justification

This study is powered for demonstrating ODI4% non-inferiority between the AutoEPAP algorithm and manual EPAP algorithm on the Astral device.

This protocol has been powered with the following inputs based on a previous study [26].

Expected mean difference in ODI: 0
 Expected standard deviation in ODI: 1.55
 Power = 80%
 Alpha = 0.05

Power to detect a difference of 1 per hour using a paired two-tailed t-test:

$$n = (Z\alpha + Z\beta)^2 \times (SD/difference)^2 = 22.84 = 23$$

Therefore, based on a crossover non-inferiority hypothesis test (one in which the outcome is dependent) we can be 95% sure that a sample size of 23 is sufficient to detect inferiority of AutoEPAP compared to with manual EPAP with respect to difference of ODI.

The update to this protocol (v3.0 to v4.0) was completed to be consistent with the recent FDA clearance of Astral with iVAPS. The increase in enrollment goal will provide additional power (95%) to detect a difference between AutoEPAP and manual EPAP.

We pre-specify a non-inferiority margin for ODI4% of 2 per hour (refer to Section 12). Basing the sample size on being able to detect the smallest difference in ODI (1 per hour) will provide greater power, through a larger sample size, in testing the non-inferiority margin (2 per hour).

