The analysis of study sites may require the formation of pseudo-sites because the small study sites will not provide appropriate information to allow the analysis above. Study sites with fewer than 6 subjects will be combined into pseudo-sites for the poolability analysis using the following method. The smallest study site with less than 6 subjects will be combined with the next smallest study site. These two sites may be combined with a third site if the combined number of patients remains less than 6. The combination of sites will be halted if combining these sites makes the new pseudo-site the largest study site. Assigned pseudo-sites will be used for the analysis of poolability described above.

4. General Statistical Analysis Guidelines

The number of observations, mean, median, standard deviation, standard error, minimum and maximum will be calculated for continuous variables, unless otherwise stated. The number of significant digits reported will be as follows: minimum and maximum will have the same number of significant digits as the raw data; the mean, median, standard deviation, and standard error will be reported with one more significant digit than the raw data. Frequencies and percentages will be calculated for categorical data using one significant digit for percentages.

As a routine function in applying statistical procedures, the assumptions underlying those procedures will be evaluated. Equal variance will be tested by Folded F-test or Levene's test depending on the number of groups being compared. Tests for normality will not be done for continuous variables, but data will be inspected for symmetry through histogram plots and severe outliers will be investigated.

5. Subject Accountability

Subjects who withdraw from the study will be tabulated with the reasons for the withdrawal. Compliance with study visits will also be presented.

6. Primary Objective and Endpoint

The primary outcome is the Oxygen Desaturation Index (ODI4%). The primary aim of this protocol is to compare ODI values following the use of the AutoEPAP algorithm with the use of manual EPAP on the Astral ventilator.

The null and alternative hypothesis is based on a non-inferiority test using a non-inferiority margin (d) of 2 events/hour.

H0: $\mu_{A-B} > d$ (new algorithm is inferior)

H1: $\mu_{A-B} \leq d$ (new algorithm is non-inferior)

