6.1. Statistical Analysis of the Primary Endpoint

The primary hypothesis will be tested using a one-sided paired t-test of the difference in ODI between Auto and Manual EPAP and compared to a non-inferiority margin for ODI4% of 2 events/hour. Additionally, the 95% upper one-sided confidence bound for the mean paired difference in ODI between manual and Auto EPAP will be calculated.

A cross-over analysis will be generated to investigate the influence of a possible period effect on the primary endpoint, paired change in ODI4% between Auto and Manual EPAP. Based on previous studies, ResMed does not expect the randomization order in which the subject used Auto versus Manual EPAP to affect the differences in ODI between the methods. A two-sample t-test comparing the two randomized treatment groups based on an alpha of 0.05 will be utilized for this analysis.

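### Protocol 6.2.4 credits 23 subjects with a 95% assurance of detecting inferiority that the design does not have, and the stated power figures do not describe the 2/h primary test

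*Protocol*

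**What the plan says.** Protocol 6.2.4 opens by saying the study is powered for non-inferiority on ODI4%. Its inputs are "Expected mean difference in ODI: 0", "Expected standard deviation in ODI: 1.55", power 80% and alpha 0.05. The calculation that follows is for a different test: "Power to detect a difference of 1 per hour using a paired two-tailed t-test". It gives n = 22.84, rounded to 23.

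Two statements with 95% in them follow. The first is said to rest on a crossover non-inferiority test: "we can be 95% sure that a sample size of 23 is sufficient to detect inferiority of AutoEPAP compared to with manual EPAP". The second explains the enlargement to 40: "The increase in enrollment goal will provide additional power (95%) to detect a difference between AutoEPAP and manual EPAP". The section ends by setting the margin at 2/h and explaining that 1/h was used to obtain a larger sample for the 2/h test.

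Protocol Section 12 tests the 2/h margin with a one-sided t-test at alpha 0.05 and attaches a power of 80% to it. It also carries another pass rule, based on a comparison of the two modes at p < 0.05: AutoEPAP passes if it is not significantly different from manual EPAP, or is significantly better.

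The SAP keeps only the margin test. SAP 6: "The null and alternative hypothesis is based on a non-inferiority test using a non-inferiority margin (d) of 2 events/hour". SAP 6.1: "The primary hypothesis will be tested using a one-sided paired t-test of the difference in ODI between Auto and Manual EPAP". SAP 10 discusses the 23 subjects and a 1/h difference. It does not repeat either 95% figure, and it gives no power against the 2/h margin.

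**The concern.** The sample-size text attributes to a non-inferiority test something such a test does not do. In the 2/h test, inferiority is the null hypothesis. The test's power is the chance of rejecting that null, which means the chance of showing non-inferiority. Failing to reject does not detect inferiority. Nor does the 95% come from the stated 80% power; it looks like 1 minus alpha described as a chance of detection.

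The other two power figures are also not attached to the right test. The 95% belongs to a difference test that the SAP does not run as its primary analysis. The 80% in Section 12 is attached to the 2/h test but does not follow from the protocol's inputs for that test. As a result, neither document tells the reader how the primary rule behaves with 36 to 40 subjects, and in particular what a pass says about a true worsening of 1/h or 1.5/h.

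**Working it through.** **Inputs.** SD 1.55, expected difference 0, sizing difference 1/h, alpha 0.05 and power 80% (Protocol 6.2.4); 36 evaluable of 40 randomized (Protocol Section 3; 40 × 0.90 = 36); margin 2/h, one-sided 0.05 (Protocol Section 12; SAP 6 and 6.1). The protocol does not say that 1.55 is the SD of the paired difference, but its paired formula uses it that way, and that is assumed here. Direction follows the SAP: AutoEPAP minus manual, against +2.

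**1. The printed n.** n = (Zα + Zβ)² × (SD/difference)², with (1.55/1)² = 2.4025.
- One-sided 0.05 gives 14.9 and two-sided 0.05 gives 18.9. The t-based values are 17 and 21. All agree with SAP 10.
- 22.84 is obtained with the Z for a tail of 0.0125 (alpha halved twice): (2.241 + 0.842)² × 2.4025 = 22.84.

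**2. The two 95% figures, as power of a two-tailed paired t-test of 1/h.** Noncentrality = 1 × √n / 1.55.
- n = 23: noncentrality 3.09, power 84.1%. So the 95% attached to 23 subjects is not the power of the named test.
- n = 36: noncentrality 3.87, power 96.4%. The normal approximation with the Z behind 22.84 gives 94.8%.
- n = 40: power 97.8%.

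The 95% for the enlarged trial therefore reproduces at 36 pairs. The sentence states no effect size; 1/h is inferred from the formula above it.

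**3. The primary rule.** Pass probability = P(T > t with n − 1 df at 0.95), where T is noncentral t with noncentrality (2 − true difference) × √n / 1.55.

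| True worsening | n = 23 | n = 36 | n = 40 |
|---|---|---|---|
| 0 | >99.9% | >99.9% | >99.9% |
| 1/h | 91.2% | 98.4% | 99.1% |
| 1.5/h | 44.2% | 60.0% | 64.1% |
| 2/h | 5% | 5% | 5% |

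Section 12 could also be read as using the bound of a two-sided 95% interval. The n = 36 column then becomes 96.4% at 1/h, 46.9% at 1.5/h and 2.5% at 2/h.

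**4. Section 12's 80%.** At a true difference of 0, power is above 99.9% at every sample size in the documents. By the normal approximation, 80% power would need (1.645 + 0.842)² × (1.55/2)² = 3.7 pairs. That is too few for the approximation to be reliable, but it shows the 80% does not describe this test at these sample sizes.

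**5. Sensitivity to the SD (n = 36, true worsening 1/h).** These SDs are assumptions; 2.19 is 1.55 × √2, which would apply if 1.55 were a single-night SD and the two nights were uncorrelated.

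| SD of paired difference | Passes 2/h rule | Two-tailed power for 1/h |
|---|---|---|
| 1.55 | 98.4% | 96.4% |
| 2.19 | 85.1% | 75.8% |
| 3.0 | 62.4% | 49.4% |
| 4.0 | 43.1% | 30.8% |

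**6. The two pass rules in Section 12.** In 400,000 simulated trials with n = 36, SD 1.55 and a true worsening of 1/h, AutoEPAP passed the 2/h rule in 98.5% and passed the rule based on no significant difference in 3.5%. In 94.9% it was both significantly worse than manual EPAP and non-inferior at 2/h, so the two rules gave opposite verdicts.

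**The case against.** The strongest reply is that the 95% power is right. It reproduces at 36 pairs for the two-tailed test that 6.2.4 names, and that power does rise with enrollment, from 84.1% at 23 pairs to 96.4% at 36. It also has a use within the protocol, because Section 12's rule on significant differences is exactly such a comparison. The choice of 1/h for sizing and 2/h for the margin is disclosed, and Section 12 gives its reasons for the margin. SAP 6 and 6.1 state the primary test clearly. No sample size, test or margin changes as a result of this point.

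All of that stands, and it limits the point. It does not rescue the statement about 23 subjects, which names the non-inferiority test as its basis and whose 95% is not the power of the two-tailed test either. It also leaves the 95% power unlabelled in a section that claims to power a non-inferiority test, and leaves Section 12's 80% unexplained.

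A reader might go further and infer that a 98% chance of passing an AutoEPAP that is 1/h worse contradicts the 95% power. The documents do not support that. These are probabilities of different events, and both can be high at once, as step 6 shows. Passing a true 1/h worsening is what a 2/h margin permits. Nor does 6.2.4 say that a pass excludes 1/h.

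**Conclusion.** The statement that 23 subjects give 95% assurance of detecting inferiority is wrong as written. The 95% power for the enlarged trial is arithmetically sound, but only as power of a two-tailed paired test of 1/h, which is not the SAP's primary analysis. Section 12's 80% does not match the protocol's own inputs for the 2/h test. What the primary rule supports, if passed, is a mean worsening below 2/h and nothing tighter.

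The figures rest on normally distributed paired differences, 36 pairs, one-sided 0.05, and 1.55 being the SD of the paired difference. The last matters most: the pass probability at 1/h falls from 98% to 62% if that SD is 3.0. This is a defect in what the plan says about its power. It does not show that the sample is too small or the margin too wide.

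**What to change.** - **Protocol 6.2.4:** delete the statement that 23 subjects suffice, with 95% assurance, to detect inferiority. Label the 95% as power of a two-tailed paired t-test of a 1/h difference that is not the SAP primary analysis.
- **Protocol 6.2.4, Protocol Section 12 and SAP 10:** replace the 80% in Section 12 and give one common statement, for example: with 36 pairs, an assumed SD of the paired difference of 1.55 and a one-sided 0.05 paired t-test against 2/h, the probability of declaring non-inferiority is above 99.9% at a true difference of 0, 98% if AutoEPAP is 1/h worse, 60% at 1.5/h and 5% at 2/h. Add the sensitivity to the SD (at 1/h: 85% if the SD is 2.19, 62% if 3.0), and say that a pass supports only a mean worsening below 2/h.
- **Protocol Section 12:** reconcile the pass rule based on no significant difference with the 2/h rule, and state which one decides.

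The cost is wording in the two documents, with no added subjects or procedures. The downside for the sponsor is that the stated sensitivity to a 1/h worsening becomes less favourable.

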6.2.5. Subject Inclusion Criteria

1. Participant has ability to provide written informed consent
2. Participants aged ≥ 18 years old
3. Participant has documented respiratory failure (e.g. sleep hypoventilation with historical PtCO₂ increase ≥ 10 mmHg) and/or daytime hypercapnia (>45 mmHg)
4. Participant is currently using non-invasive positive pressure ventilation in ST or VAPS mode for ≥ 3 months
5. Participants with a previously documented AHI ≥ 5 /hr
6. Participants with a recently (≤ 12 months ago) reviewed EPAP setting

6.2.6. Subject Exclusion Criteria

1. Participants are not compliant on NIPPV (e.g. < 4 hr/night)
2. Participants who are pregnant
3. Participants on oxygen therapy ≥ 5 L/min
4. Participants with an invasive interface (e.g. tracheostomy)
5. Participants who have had an acute exacerbation within the last 3 months that resulted in a hospitalisation
6. Participants who are acutely ill, medically complicated or who are medically unstable
7. Participants in whom NIPPV therapy is otherwise medically contraindicated
8. Participants who have had surgery of the upper airway, nose, sinus, or middle ear within the previous 90 days
9. Participants with untreated, non-OSA sleep disorders, including but not limited to; insomnia, periodic limb movement syndrome, or restless legs syndrome.
10. Participants who have the following pre-existing conditions: severe bullous lung disease, recurrent pneumothorax or pneumomediastinum, cerebrospinal fluid leak, recent cranial surgery or trauma.
11. Participant does not comprehend English
12. Participant is unable or unwilling to provide written informed consent

13. Participant is physically and/or mentally unable to comply with the protocol
14. Participant is not suitable to participate in the trial for any other reason in the opinion of the investigator

7. STUDY DEVICES

ResMed (ResMed, Sydney, Australia, K152068) is a developer, manufacturer and distributor of medical device equipment, including the Astral device which is designed for treating patients with respiratory disorders. ResMed is also the manufacturer responsible for the iVAPS and AutoEPAP algorithms.

7.1. Astral device

The ResMed “Astral” device is a mixed mode ventilator and for this protocol will provide mechanical ventilation. The Astral device will have iVAPS with manual EPAP and AutoEPAP algorithms, and the clinician will have the ability to manually change between the two modes.

The Astral device will deliver positive airflow to the patient via approved tubing and a vented mask. The device will therefore only come into direct contact with the surface of the skin, primarily the hands, during movement, setup, or adjustment of the device.

For the purpose of this clinical trial, user and clinical guides (Appendix A) will be provided with the devices to the clinicians and participants which will include iVAPS AutoEPAP specifications.

The iVAPS AutoEPAP algorithm is currently not approved by the FDA, and is therefore considered an Unapproved Medical Device.

7.2. Device Accountability

An accurate and current accounting of the dispensing of ResMed devices (Astral) will be maintained on an on-going basis by a qualified member of the study site using the Sponsor-provided “Device Disposition Log”. The serial number unique to each Astral device will be documented on this Log. Devices will be made available to the investigator by ResMed. If a replacement device is dispensed, it will be documented per device accountability procedure. All non-disposable ResMed devices must be returned to ResMed at the end of the study.

7.3. Labeling

The label contains the information as required by relevant regulatory requirements:

- a) Sponsor name and address
- b) Serial number to identify the individual device
- c) Instruction For Use

7.4. Packaging

The Astral device is FDA 510(k) cleared (K152068) and will be used with the standard packaging. “Investigational Use Only” stickers will be placed on all study devices prior to sending to study sites.

7.5. Instruction for Use

The devices will be used as specified in the relevant Instructions for Use provided by ResMed Corp.

For the purpose of this clinical trial, the Astral device is intended to treat stable patients with respiratory failure and who weigh at least 30 kg..

7.6. Required Training

Subjects will be instructed on usage of the devices by the local Investigators or designee. ResMed will provide the investigators' training.

All staff involved in the clinical trial will be experienced in the operation and set-up of NIPPV devices and PSG. The site will be provided with User and Clinical Guides to assist with device setup and operation.

It is expected that the trial site will use their usual equipment for conducting overnight pressure determination PSGs for the purpose of the investigational sleep studies. Therefore, it is not anticipated that any additional training on using the study equipment is required for the trial site.

Prior to the commencement of the study, the Sponsor will educate the investigators and site coordinators on the protocol, including data collection and data management. The Sponsor will educate the investigators and site coordinators on any protocol amendments and updates.

8. THERAPY

8.1. Treatment with Astral device

During this study, the Astral device will be used in a clinic setting during monitored PSG testing. AutoEPAP and manual EPAP will be used in iVAPS mode for this study.

8.2. Set up of Astral device

For initiation of therapy, for subjects in either arm of the study, the Astral device will be set with clinically appropriate settings, as determined by the treating physician and investigator. These settings include: target volume and minimum and maximum pressure support (PS). For subjects randomized to the manual EPAP group on Visit 2, the EPAP settings will be based on the subject's previous titrated settings. For subjects randomized to the AutoEPAP group on Visit 2, the minimum and maximum AutoEPAP settings will be set to default, or as clinically appropriate. Additional details and instructions will be included in the study Manual of Procedures.

9. STUDY SCHEDULE

A summary of the procedure is summarized in Figure 2.

Figure 2. Summary of trial procedure

Visit 1

- Provide consent
- Meet eligibility criteria
- Collect baseline data

9.1. Visit 1

Participants will be recruited from existing hospital patient databases. Participants will be pre-screened and those meeting the required criteria will be contacted by the investigators via follow up phone call or during an office visit, and asked if they wish to take part in the study.

Participants wishing to participate will attend the sleep clinic/hospital where written informed consent will be obtained (Appendix B). All participants will be checked for study eligibility using the Inclusion/Exclusion criteria of this protocol. Participants who do not meet the eligibility criteria will not be included in the study. Participants meeting the eligibility criteria will have baseline information collected, including participant demographics, medical history, and information about the participants' current therapy. If available, the following information will also be collected into the subject chart: diagnostic sleep study report, their most recent spirometry report, and at the physicians' discretion, a capillary blood gas test.

9.2. Visit 2

Participants will attend an office visit where they will be randomized (1:1) to receive iVAPS with AutoEPAP or iVAPS with manual EPAP first. Participants will be randomized according to a computer-generated randomized list.

Participants will undergo an overnight PSG at the site per their randomized group assignment. Full PSG set-up, data acquisition, monitoring and reporting will be performed using the AASM 2007 criteria. Therapy will be delivered using the clinical trial device, Astral. At least 4 hours of recording will be required.

Participants' trial devices will be setup according to the therapy settings detailed in the Therapy section of this protocol. The set-up of manual EPAP or AutoEPAP settings shall occur before lights out. Study staff will also set up the subject to test PtCO₂. This may be done with a device clipped to the outside of the subject's ear, and does not introduce risk to the subject.

Ensure a new USB flash drive is labelled and inserted into the Astral device prior to the commencement of the study. The device's ID number is to be recorded in the CRF before the end of the visit. Ensure there is an SD card in the machine, and the SD card is labelled with the participant ID number, therapy type, Night 1.

Visit 1 and 2 may be conducted on the same day.

9.2.1. Visit 3

Participants will undergo an overnight PSG at the site per their randomized group assignment. Full PSG set-up, data acquisition, monitoring and reporting will be performed using the AASM 2007 criteria. Therapy will be delivered using the clinical trial device, Astral. At least 4 hours of recording will be required.

Participants' trial devices will be setup according to the therapy settings detailed in the Therapy section of this protocol. The set-up of manual EPAP or AutoEPAP settings shall occur before lights out. Study staff will also set up the subject to test PtCO₂. This may be done with a device clipped to the outside of the subject's ear, and does not introduce risk to the subject.

Ensure a new USB flash drive is labelled and inserted into the Astral device prior to the commencement of the study. The device's ID number is to be recorded in the CRF before the end of the visit. Ensure there is an SD card in the machine, and the SD card is labelled with the participant ID number, therapy type, Night 2.

The completion of Visit 3 marks the completion of study participation. Participants will return to their usual NIPPV therapy and have the option of keeping the mask and chinstrap that was used during the study.

9.3. Study Completion

PSG scoring will be centralized to ensure scoring consistency across sites. De-identified scored PSGs, Astral devices and flash cards will be returned to the Sponsor following study completion.

Data analysis will be performed by an independent statistician.

A final study report will be prepared by ResMed's Medical Affairs department.

10. STUDY TIMELINE

The investigators estimate it will take up to 16 weeks to recruit a total of 40 participants from all US sites.

Each participant is to attend 2-3 visits to the site (Visit 1 and 2 may be combined). Visits 2 and 3 will be overnight visits at the site's sleep unit. Ideally, sleep studies will occur on 2 consecutive nights. However, it is permitted that Night 2 can occur within 1 week from Night 1.

Therefore, the duration of the study is expected to take approximately 5 months to complete. This time frame also accounts for data monitoring, analysis and the development of the clinical study report.

